5.5 APPENDIX 5 CRITERIA FOR POTENTIALLY CLINICALLY SIGNIFICANT ABNORMALITIES

Table 12 - Criteria for Potentially Clinically Significant Abnormalities

Parameter	PCSA
Clinical Chemistry	
ALT	By distribution analysis : >3x ULN >5x ULN >10x ULN >20x ULN
ALT and Total Bilirubin	ALT >3x ULN and TBILI >2x ULN

Parameter	PCSA
eGFR (mL/min/1.73 m ²) (Estimate of GFR based on an MDRD equation)	<10 <15 (kidney failure) ≥40% decrease in eGFR from baseline ≥50% decrease in eGFR from baseline
Creatinine	≥100% change from baseline
Albumin (g/L)	Change from baseline to: <30 ≥30 >300
Vital signs	
HR (bpm)	≤50 and decrease from baseline ≥20 ≥120 and increase from baseline ≥20
SBP (mmHg)	≤95 and decrease from baseline ≥20 ≥160 and increase from baseline ≥20
DBP (mmHg)	≤45 and decrease from baseline ≥10 ≥110 and increase from baseline ≥10
Weight	≥5% increase from baseline ≥5% decrease from baseline

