13.4 Appendix: Clinical Safety Laboratory Tests

- The tests detailed in [Table 13-4](#) will be performed at the central laboratory, except urine pregnancy tests, which will be performed at sites using urine pregnancy test kits that are provided by PPD.
- Protocol-specific requirements for inclusion or exclusion of patients are detailed in [Section 4](#) of the protocol.
- Additional tests may be performed at a local or central laboratory at any time during the trial as deemed necessary by the investigator or required by local regulations. If a test is used to evaluate an AE (diagnostic, follow-up, outcome), the results (including notably, the disease progression of CKD) must be entered into the eCRF.

Table 13-4 Protocol-Required Safety Laboratory Assessments

Laboratory Assessments ^a	Parameter
Hematology	Erythrocytes
	Platelet count
	Leukocytes
	Hb
	Hematocrit
Clinical chemistry	AST
	ALT
	Alkaline phosphatase
	Total bilirubin (if >ULN, then the direct and indirect subfractions must be measured)
	Albumin (serum)
	Creatinine (serum) ^b
	Spot urine albumin: creatinine ratio ^b
	eGFR ^{b,c}
	Sodium
	Potassium
Urinalysis	pH
	Glucose
	Ketones
	Leukocytes
	Blood/Hb
	Protein

Abbreviations: ALT, alanine aminotransferase; AST, aspartate aminotransferase; CKD, chronic kidney disease; CKD-EPI, Chronic Kidney Disease Epidemiology Collaboration; cr, creatinine; eCRF, electronic case report form; eGFR, estimated glomerular filtration rate; Hb, hemoglobin; MDRD, Modification of Diet in Renal Disease; Scr, serum creatinine; ULN, upper limit of normal.

^a All protocol-required safety laboratory assessments will be performed at the central laboratory, except urine pregnancy tests, which will be performed locally; the results of each test must be entered into the eCRF.

^b Creatinine and eGFR (clinical chemistry) and spot urine albumin: creatinine ratio will be measured for CKD monitoring.

^c The central laboratory should calculate eGFR using the CKD-EPI equation: $eGFR_{cr} = 142 \times \min(\text{Scr}/\kappa, 1)^a \times \max(\text{Scr}/\kappa, 1)^{-1.200} \times 0.9938^{\text{Age}} \times 1.012$ [if female] ([National Kidney Foundation 2022](#)).

13.5 Appendix: Adverse Events: Definitions and Procedures for Recording, Evaluating, Follow-Up, and Reporting

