4.7.4 Additional safety assessments

4.7.4.1 Laboratory variables and vital signs

The following laboratory variables and vital signs variables will be analyzed from baseline to Week 24 per [Section 5.7](#). They will be converted into standard international units.

- Hematology:
 - Red blood cells and platelets: erythrocytes, platelet count, leukocytes, hemoglobin, hematocrit
- Clinical chemistry:
 - Metabolism: albumin
 - Electrolytes: sodium, potassium
 - Renal function: creatinine, eGFR, creatinine clearance. Creatinine clearance will be derived with the equation of Cockcroft and Gault using weight assessed at the same visit as creatinine. The central laboratory should calculate eGFR using the Chronic Kidney Disease Epidemiology Collaboration (CKD-EPI) equation:
$$\text{eGFR}_{\text{Cr}} = 142 \times \min(\text{Scr}/\kappa, 1)^\alpha \times \max(\text{Scr}/\kappa, 1)^{-1.200} \times 0.9938 \times \text{Age} \times 1.012$$
 [if female](6).
 - Liver function: ALT, aspartate aminotransferase (AST), alkaline phosphatase (ALP), total bilirubin, indirect bilirubin, direct bilirubin

- Urinalysis:
 - Quantitative analysis: pH, protein, ketones, leukocytes, blood/hemoglobin, glucose
- Pregnancy test: urine or serum
- Vital signs: body weight, heart rate, systolic blood pressure (SBP) and diastolic blood pressure (DBP) while in seated position

The tests detailed above will be performed at the central laboratory, except urine pregnancy tests, which will be performed at sites using urine pregnancy test kits that are provided by PPD. Additional tests may be performed at a local or central laboratory at any time during the trial, as deemed necessary by the investigator or required by local regulations. If a test is used to evaluate an AE (diagnostic, follow-up, outcome), the results (including the disease progression of CKD) must be entered into the CRF.

All laboratory tests with values that are considered clinically significantly abnormal during the trial should be repeated until the values return to normal/baseline or are no longer considered clinically significant by the investigator. Potentially clinically significant abnormalities (PCSA) will be flagged and the number and percentage of participants with PCSA will be presented.

Quantitative analyses

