For all laboratory variables and vital signs above, descriptive statistics for results and changes from baseline will be provided for each analysis window, as well as the last value and the worst value (minimum and/or maximum value depending on the parameter) during the on-treatment period. These analyses will be performed using central measurements only (when available) for laboratory variables. A scatter plot of the worst post-baseline treatment-emergent value vs baseline value will also be presented by biological function and parameter.

Analyses according to PCSA

PCSA analyses will be performed based on the PCSA list in [Section 5.5](#). For parameters for which no PCSA criteria are defined, similar analyses will be done using the normal range, if applicable.

Analyses according to PCSA will be performed based on the worst value during the treatment-emergent period, using all measurements (either local or central, either scheduled, nonscheduled or repeated).

For laboratory variables and vital signs variables above, the incidence of participants with at least one PCSA during the treatment-emergent period will be summarized regardless of the baseline level and according to the following baseline status categories:

- Normal/missing
- Abnormal according to PCSA criterion or criteria

In addition to summary tables, the percentage (%) of participants with at least one abnormality (PCSA) during the treatment-emergent period will be presented using bar charts, by biological function and parameter.

4.7.4.2 *Product complaints*

All product complaint summaries during the on-treatment period (defined in [Section 4.1](#)) will be generated in the safety population and will include the number (%) of participants experiencing at least one event, the number of events and rate per participant-year.

The event rate per participant-year will be defined as the number of events divided by the cumulative duration of all participants' exposure expressed in years.

The overview of product complaints with the details below will be generated:

- Any product complaint
- Any product complaint related to AEs
- Any product complaint leading to incorrect IMP dose administration

In addition, the analyses below will be conducted.

- Any product complaint categorized by type of complaint
- AE(s) leading to product complaints by primary SOC and PT

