5.7 SCHEDULE OF EVENTS

5.7.1 Schedule of events for the main trial

Table 13 - Schedule of events for the main trial

Trial Period	Screening	Baseline/ Randomization	Treatment											Follow-Up
			Titration ^a						Maintenance					
Visit ^b	1	2	3–5	6	7–9	10	11–13	14	15	16	17 ^c	Unscheduled ^d	18	
Visit Type	Clinic	Clinic	Phone	Clinic	Phone	Phone	Phone	Clinic	Phone	Phone	Clinic	Clinic or Phone	Phone ^e	
Week	-2	0	1 to 3	4	5 to 7	8	9 to 11	12	16	20	24			25
Day	-14	0	1 to 21	28	35 to 49	56	63 to 77	84	112	140	168			175
Window (Days)	±2	±2		±3		±3		±3	±3	±3	±3			±3
Informed consent	X													
Inclusion and exclusion criteria	X	X												
Randomization		X												
Demography (including height)	X													
Medical/Surgical history	X													
Prior/Current medications	X													
Physical examination ^f	X	X									X			
Study drug dispensing		X		X		X ^g		X			X			
SoloStar or FlexTouch pen instruction ^h		X												
Patient eDiary setup	X													
Patient eDiary completion	<-----X----->													
Collection of eDiary		X		X				X			X	X		
Glucose meter (dispensing and instruction)	X													

Trial Period	Screening	Baseline/ Randomization	Treatment											Follow-Up
			Titration ^a						Maintenance					
Visit ^b	1	2	3–5	6	7–9	10	11–13	14	15	16	17 ^c	Unscheduled ^d	18	
Visit Type	Clinic	Clinic	Phone	Clinic	Phone	Phone	Phone	Clinic	Phone	Phone	Clinic	Clinic or Phone	Phone ^e	
Week	-2	0	1 to 3	4	5 to 7	8	9 to 11	12	16	20	24			25
Day	-14	0	1 to 21	28	35 to 49	56	63 to 77	84	112	140	168			175
Window (Days)	±2	±2		±3		±3		±3	±3	±3	±3			±3
Collection of glucose meter (if mandatory by local regulation)												X		
Daily dosing of Gla-300 or IDeg-100 ⁱ			<-----X----->											
Study drug dose adjustments			X	X	X	X	X	X	X	X	X			
Concomitant medications		X	X	X	X	X	X	X	X	X	X			X
Study drug adherence and accountability				X				X				X		
HbA1c	X	X						X				X		
FPG ^j	X	X						X				X		
Fasting SMPG ^k			<-----X----->											
7-point SMPG ^l		X						X				X		
Hypoglycemia events ^m	X	X	X	X	X	X	X	X	X	X	X			X
Recording of AEs and SAEs (including AESIs)	X	X	X	X	X	X	X	X	X	X	X	X		X
Product complaints		X	X	X	X	X	X	X	X	X	X	X		
Vital signs (including body weight) ⁿ	X	X						X				X		
Clinical chemistry ^o	X ^p											X ^p		
Hematology ^o	X													
Urinalysis ^o	X													
Spot urine albumin: creatinine ratio	X ^p											X ^p		
Pregnancy test ^q	X			X				X			X			

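### The albumin row of SAP Table 12 counts a recovery in serum albumin as an abnormality and includes a cut-off that serum cannot reach

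*SAP*

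**What the plan says.** SAP Appendix 5 (Section 5.5), Table 12, has a row for albumin with the unit g/L. Its PCSA criterion is "Change from baseline to: <30 ≥30 >300".

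SAP 4.7.4.1 lists the variables to which the PCSA analyses apply. Albumin appears once, under clinical chemistry, as "Metabolism: albumin". The renal entry there reads "Renal function: creatinine, eGFR, creatinine clearance", and the urinalysis entry contains no albumin. Protocol Table 13-4 has one plain albumin entry, specified as serum, and a separate entry for the urine ratio. The schedule in SAP Table 13 includes "Spot urine albumin: creatinine ratio" at screening and Week 24.

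PCSAs are counted as participants with at least one event, based on the worst treatment-emergent value, both overall and by baseline status (normal or missing versus abnormal by the PCSA criterion). SAP 4.7.4.1 also has a fallback: "For parameters for which no PCSA criteria are defined, similar analyses will be done using the normal range, if applicable".

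**The concern.** A PCSA criterion should pick out values that have moved in a harmful direction or passed a harmful limit. The change criteria elsewhere in Table 12 mostly do so explicitly. The eGFR row, for example, uses "≥40% decrease in eGFR from baseline", and the heart rate, blood pressure and weight rows each say increase or decrease. The creatinine row asks for a change of at least 100%, which in practice can only be a rise.

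The albumin row names both sides of the same limit, <30 and ≥30, as destinations that count. For serum albumin the low side is the concern, so a change to ≥30 g/L is an improvement. The third cut-off, >300 g/L, is not a possible serum value. At stake is whether an albumin PCSA count by arm, in a population with renal impairment, can be read as a count of deterioration.

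**Working it through.** The plan gives no figure to reproduce, so the check is to apply the printed cut-offs to serum values under each plausible reading.

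**Inputs.** The cut-offs <30, ≥30 and >300 and the unit g/L come from SAP Table 12. The analyte, serum albumin, comes from SAP 4.7.4.1 read with protocol Table 13-4. The counting rule comes from SAP 4.7.4.1. One assumption is added: serum albumin lies between 15 and 55 g/L. Any plausible range leads to the same conclusion, because only the position relative to 30 matters and 300 is never approached.

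**Reading 1: cut-offs pooled, flag if the category changes from baseline.** Serum can occupy two of the three categories, which gives four combinations:

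| Baseline | On treatment | Example (g/L) | Flagged | Meaning |
|---|---|---|---|---|
| ≥30 | ≥30 | 42 to 41 | no | stable |
| <30 | <30 | 26 to 25 | no | stays low |
| ≥30 | <30 | 32 to 28 | yes | fall |
| <30 | ≥30 | 28 to 32 | yes | recovery |

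One of the two flagged combinations is a recovery. On whole numbers from 15 to 55 there are 15 values below 30 and 26 at or above it, so 41 × 41 = 1,681 pairs. Flagged pairs are 15 × 26 + 26 × 15 = 780, of which 15 × 26 = 390 are recoveries. The one-half share follows from the symmetry of the grid. It shows the logic and does not estimate what the trial would have seen.

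**Reading 2: each cut-off is a separate line.**
- Change to <30: only a fall from ≥30 qualifies. This line is usable.
- Change to ≥30: only a rise from <30 qualifies, so every participant on this line has recovered.
- Change to >300: 0 of the 41 values qualify, so the line is empty.

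**Does the worst-value rule repair it?** No. Taking the minimum as worst, a participant at 28 g/L at baseline whose lowest later value is 32 g/L has still moved to ≥30. Clinical chemistry is scheduled only at screening and Week 24, so there is often just one later value to choose from.

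**Does a lost upper bound explain it?** No. If the middle category was meant to be 30 to 300, every serum value of 30 or more still falls inside it, and the counts of 780 and 390 do not change.

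**Reading 3: the row was meant for the urine albumin:creatinine ratio.** Upward crossings of 30 and 300 would then be a coherent scheme, but the label and the unit g/L would both be wrong, and the ratio is missing from the variable list in SAP 4.7.4.1.

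**The case against.** The best defence is Reading 2. Other cells of Table 12 hold several criteria that need not be pooled: the ALT row has four multiples of the upper limit, and the weight row holds opposite directions. The table may also have lost its line breaks in conversion. On that view the <30 line is a sound low-albumin criterion, and each line has an implied direction. This stands, and it rules out saying that the row cannot identify low albumin at all. It does not rescue the ≥30 and >300 lines.

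The split by baseline status also helps in part. If baseline <30 is classed as abnormal, falls and recoveries land in different strata, and only the overall count mixes them. Under pooling, however, every flag in the abnormal-baseline stratum is then a recovery. The SAP also does not say how a change criterion is to class a baseline value.

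Three stronger readings are tempting, and the documents do not support them:
- A reader might infer that every participant would be flagged, since every number is either <30 or ≥30. That ignores the row's wording about change from baseline. Under a change rule stable values are not flagged.
- A reader might infer that serum albumin has lost the normal-range fallback. That follows only if the row really defines a serum criterion. If the urine ratio was meant, no serum criterion exists and the fallback still covers serum albumin.
- A reader might infer that the urine ratio goes unanalysed. It is not named in SAP 4.7.4.1, but the exploratory sections are redacted and could contain it.

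Finally, the trial was stopped on 27 June 2023, before the SAP was approved on 17 October 2023. The output list in SAP Appendix 6 contains no laboratory PCSA table, figure or listing. That limits the consequence and is accepted in full.

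**Conclusion.** The row is wrong as written for serum albumin, and no reading of it is fully right. Pooled, it flags recoveries together with falls. Line by line, one of its three lines works, one counts recovery and one is empty. If the urine ratio was intended, the analyte and unit are mislabelled. The conclusion rests on albumin in SAP 4.7.4.1 being serum, as protocol Table 13-4 indicates, and on serum values never nearing 300 g/L.

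The size is small. Only descriptive PCSA displays for albumin are affected. SAP 4.7.4.1 separately promises that "descriptive statistics for results and changes from baseline will be provided for each analysis window", along with last and worst values, and those summaries are sound. No Appendix 6 output for the abbreviated report changes. The share of flags that would be recoveries cannot be estimated, because the documents give no albumin mean, spread or correlation.

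**What to change.** For serum albumin, either keep a single criterion, a fall from ≥30 g/L at baseline to <30 g/L, and drop the ≥30 and >300 cut-offs, or delete the row so that the normal-range rule in SAP 4.7.4.1 applies.

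The sponsor should also state which analyte and unit the row was meant for. If it confirms the urine albumin:creatinine ratio, relabel the row with that unit, flag upward shifts only (from <30 to ≥30, and from ≤300 to >300), and add the ratio to the renal function list in SAP 4.7.4.1.

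The cost is one corrected table row and at most one added list entry. No new samples or data are needed, and the abbreviated report's outputs stay as they are.

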5.6 APPENDIX 6 TABLE OF CONTENTS FOR ABBREVIATED CSR

	Title	Analysis Set
Table		
14.1.1.1	Participant Disposition	ITT Set
14.1.1.2	Analysis Sets	Screened Set
14.1.1.3	Number of Participants Screened	Screened Set
14.1.1.4	Number of Participants Screened by Country and Site	Screened Set
14.1.2	Significant Protocol Deviations	ITT Set
14.1.3.1	Demographics and Participant Characteristics at Baseline	Safety Set
14.1.3.2	Disease Characteristics at Baseline	Safety Set
14.1.4	Medical or Surgical History at Screening by Primary SOC and PT	ITT Set
14.1.5.1	Extent of Study Treatment Exposure	Safety Set
14.1.5.2	Treatment Compliance	Safety Set
14.1.5.3	Dosing Summary	Safety Set
14.2.1.1	Baseline Summary of Primary Endpoint: HbA1c Level	ITT Set

	Title	Analysis Set
14.2.1.2	Baseline Summary of Primary Endpoint: HbA1c Level by Subgroups	ITT Set
14.2.2.	Baseline Summary of Secondary Endpoints	ITT Set
14.3.1	Overview of Adverse Event profile: Treatment-emergent Adverse Events	Safety Set
14.3.2	Number (%) of Participants with TEAE(s) by Primary SOC, HLGT, HLT and PT	Safety Set
14.3.3.	Participants with a Common TEAE ($\geq 5\%$) in Any Treatment Group by Primary SOC, HLGT, HLT and PT	Safety Set
14.3.4	Number (%) of Participants with TEAE(s) Related to IMP as per Investigator's Judgment by Primary SOC and PT	Safety Set
14.3.5	Number (%) of Participants with Treatment-emergent SAEs by Primary SOC and PT	Safety Set
14.3.6	Number (%) of Participants Who Died by Study Period	Safety Set
14.3.7	Overview of Hypoglycemic Events Overall and by Observation Period, ADA Level, and Diurnal Distribution	Safety Set
Figure		
14.2.1.1	Box Plot of HbA1c Level by Analysis Visit (Observed Cases)	ITT Set
14.2.2.1	Box Plot of FPG Level by Analysis Visit (Observed Cases)	ITT Set
14.2.2.2	Box Plot of SMPG Level by Analysis Visit (Observed Cases)	ITT Set
14.2.2.3	Line Plot of 7-point SMPG Profiles, Per Time Point within 24-Hour Period by Analysis Visit (Observed Cases)	ITT Set
14.2.2.4	Bar Chart of Percentage (%) of Participants Reaching HbA1c $< 7.0\%$ at Week 24 (Observed Cases)	ITT Set
Listing		
16.2.1	Participant Randomization List	ITT Set
16.2.2	Listing of Participants with at Least One Protocol Deviation	ITT Set
16.2.3.1	Listing of Participant Demographics	Safety Set
16.2.3.2	Listing of Baseline Disease Characteristics	Safety Set
16.2.5.1	Exposure to IMP	Safety Set
16.2.7.1	Listing of all AEs	Safety Set
16.2.7.2	Listing of all AEs leading to study discontinuation	Safety Set
16.2.7.3	Listing of All Participants who Died During the Study	Safety Set
16.2.7.4	Listing of On-treatment Hypoglycemic Events	Safety SEt
16.2.8	Listing of Participants with HbA1c, SMPG, or FPG values at Week 24	ITT Set

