4 STATISTICAL ANALYSES

4.1 GENERAL CONSIDERATIONS

Due to early termination of the study, the analyses described in this SAP were not performed in totality due to lack of data and in accordance with the abbreviated CSR (clinical study report). See Appendix 2 ([Section 5.2](#)): Changes to protocol-planned analyses for additional details.

In general, continuous data will be summarized using the number of observations available, mean, SD, median, Q1, Q3, minimum, and maximum.

All mean, SD, median, Q1 and Q3 values will be formatted to one more decimal place than the measured value. Minimum and maximum will be formatted to the same number of decimal places as the measured value.

Categorical data will be summarized using frequency counts and percentage of participants. When count data are presented, the percent will be suppressed when the count is zero to draw attention to the non-zero counts. A row denoted 'Missing' will be included in count tabulations for demographics, baseline characteristics and compliance to account for missing values. No percentages will be displayed on the 'Missing' rows and the percentages on the other rows will be based on the number of non-missing observations. Unless otherwise specified, the denominator for all other percentages will be the number of participants in that treatment within the specific analysis set of interest. All percentages will be rounded to one decimal place. The number and percentage of responses will be presented in the form xx (xx.x), where the percentage is in the parentheses. When the numerator is equal to the denominator, the percentage should be presented as (100) instead of (100.0), unless otherwise specified.

All CIs presented will be 2-sided 95% CIs, unless otherwise specified, and will be displayed to the same level of precision as the statistic they relate to. If an estimate or a CI is not estimable, it will be presented as 'NE'. If neither an estimate, nor its CI are estimable, it will be presented as simply 'NE', not displaying 'NE' twice.

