- Step 2 will test superiority of Gla-300 versus IDeg-100 if noninferiority of Gla-300 versus IDeg-100 as described above has been demonstrated. The superiority of Gla-300 versus IDeg-100 will be established if the 95% CI for the difference in mean change from baseline to Week 24 in HbA1c level between Gla-300 and IDeg-100 lies entirely below 0%. If non-inferiority has been established but the superiority is not met, the declaration of non-inferiority will be further supported by a supplementary estimand as described in [Section 4.3.4](#).

There is no multiplicity argument that affects switching between non-inferiority and superiority in the analysis of the primary endpoint, since both are based on the same estimand and it therefore corresponds to a simple closed testing procedure. If superiority for the primary endpoint (change from baseline to Week 24 in HbA1c level) is achieved, secondary endpoints will be assessed for superiority and adjusted for Type I error related to multiple testing using the Holm procedure as described in [Section 4.6](#). Control of Type I error will be limited to the primary and key secondary efficacy endpoints for the overall population. No statistical claim will be made on the exploratory efficacy endpoints (including the CGM substudy endpoints), nor for subgroup analyses.

All safety analyses will be performed on the safety set.

In general, descriptive statistics of quantitative efficacy and safety parameters (result and absolute change from baseline) by analysis visits will be provided on observed cases (OC; ie, inclusion of only participants having non-missing assessments for a specific analysis visit). Descriptive summaries of continuous efficacy and safety data at baseline will be included when presenting descriptive summaries of the corresponding changes from baseline, where appropriate. Unless otherwise specified, analyses will be performed by intervention group (and overall for baseline and demographics characteristics).

Despite the open-label administration of the study drugs, all statistical analyses outlined in this plan prior to final database lock will be developed and performed blindly. A process will be

applied to ensure blinding of Gla-300 and IDeg-100 administrations and any potentially unblinding information.

All statistical analyses will be performed using SAS software Version 9.4 or higher.

Observation period

The observation period will be divided into 3 segments for non-safety analyses:

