4.3 PRIMARY ENDPOINT ANALYSIS

4.3.1 Definition of endpoint

The primary endpoint is the change from baseline to Week 24 in HbA1c level. For efficacy assessments of the trial, HbA1c will be measured with blood samples collected at the central laboratory at the time points specified in [Section 5.7](#) (baseline, Week 12, Week 24). If a participant needs to receive a rescue antidiabetic therapy, the HbA1c assessment should be performed before the antidiabetic therapy is introduced. In addition, in case of study drug treatment discontinuation, participants will be followed up per protocol. In case of trial discontinuation, HbA1c assessment will be performed at the time of withdrawal. If HbA1c measurements fall out of windowed assessments (baseline, Week 12, Week 24), the results for those assessments will be excluded (considered as missing for analysis).

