5.2 APPENDIX 2 CHANGES TO PROTOCOL-PLANNED ANALYSES

Changes to protocol-planned analyses include the following:

- Multiplicity adjustments on secondary endpoints ([Section 4.1](#), [Section 4.4.1.2](#), [Section 4.6](#)).
- ~~CCI~~ compliance rules ([Section 4.5.1](#)).
- Analysis of exploratory endpoints - ~~CCI~~ ([Section 4.5.2](#)).

Due to study early termination, planned analyses have been reduced in accordance with an abbreviated CSR. The list of tables, listings and figures supporting the abbreviated CSR are documented in Appendix 6 ([Section 5.6](#)) and focus on demographics, disease characteristics at baseline, exposure, participant disposition and safety. Primary and secondary efficacy data is descriptively summarized.

5.3 APPENDIX 3 DEMOGRAPHICS AND BASELINE CHARACTERISTICS, MEDICAL (OR SURGICAL HISTORY), DISEASE CHARACTERISTICS AT BASELINE, PRIOR AND CONCOMITANT MEDICATIONS

The following demographics and baseline characteristics, medical and surgical history and disease characteristics at baseline, and prior and concomitant medications will be summarized for the ITT population. Continuous data will be summarized using descriptive statistics. Categorical data will be summarized using counts and percentages.

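### By title, the abbreviated report's efficacy tables stop at baseline, and no output reports change in HbA1c from baseline to Week 24, the primary endpoint

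*SAP*

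**What the plan says.** SAP Section 4.3.1 defines the endpoint: "The primary endpoint is the change from baseline to Week 24 in HbA1c level".

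SAP Section 4.1 opens with the reduction in scope: "Due to early termination of the study, the analyses described in this SAP were not performed in totality due to lack of data", and refers to Appendix 2. Later in the same section, as a general rule, "descriptive statistics of quantitative efficacy and safety parameters (result and absolute change from baseline) by analysis visits will be provided on observed cases". That section also says that baseline summaries accompany the corresponding change summaries. It defines a continuous summary as the number of observations, mean, SD, median, Q1, Q3, minimum and maximum.

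SAP Appendix 2 (Section 5.2) says that the reduced report concentrates on demographics, baseline disease characteristics, exposure, disposition and safety, and then: "Primary and secondary efficacy data is descriptively summarized". It also states: "The list of tables, listings and figures supporting the abbreviated CSR are documented in Appendix 6".

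SAP Appendix 6 (Section 5.6) lists three efficacy tables, all on the ITT set:
- 14.2.1.1, "Baseline Summary of Primary Endpoint: HbA1c Level"
- 14.2.1.2, "Baseline Summary of Primary Endpoint: HbA1c Level by Subgroups"
- 14.2.2, the same kind of baseline summary for the secondary endpoints

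**The concern.** Section 4.1 treats the baseline summary as the companion of the change summary. Appendix 6 keeps the companion and drops the change. If it is followed exactly, the report of a randomized trial gives no n, mean or SD by arm for its primary endpoint, and none for the continuous secondary endpoints after baseline. A reader must take post-baseline levels from plots, or rebuild the Week 24 change from patient listings. When few patients contribute, a box plot without a tabulated n can also suggest more information than there is.

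**Working it through.** No figure in the plan needs reproducing. The check sets the Appendix 6 titles against the endpoint definition, Appendix 2 and Section 4.1.

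**1. Count of outputs.** Appendix 6 lists 21 tables, 5 figures and 10 listings: 21 + 5 + 10 = 36.

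| Output type | Efficacy outputs | Post-baseline efficacy, by title | Change from baseline, by title |
|---|---|---|---|
| Tables | 14.2.1.1, 14.2.1.2, 14.2.2 | 0 of 3 | 0 |
| Figures | 14.2.1.1, 14.2.2.1 to 14.2.2.4 | 5 of 5, observed cases | 0 |
| Listings | 16.2.8 | 1 of 1, Week 24 only | 0 |

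Three of the five figures are box plots of HbA1c, FPG and SMPG level. One is a line plot of the 7-point profile, and one is a bar chart of HbA1c below 7.0%.

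**2. What the retained tables add.** SAP Section 5.3.3 already places baseline HbA1c, FPG and SMPG among the disease characteristics, reported in Table 14.1.3.2 on the Safety set. Tables 14.2.1.1 and 14.2.2 largely repeat them on the ITT set.

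**3. What can be rebuilt.** Going by titles, Week 24 change by arm needs three listings joined: 16.2.1 (randomization), 16.2.3.2 (baseline disease characteristics, Safety set) and 16.2.8 (Week 24 values). Week 12 HbA1c and FPG are in no listing by title. They appear only in the box plots.

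**4. The responder endpoint.** SAP Section 4.4.1.1 calls for the number and percentage below 7.0%, counting a missing Week 24 value as not reached. The only output in Appendix 6 is an observed-case bar chart, which uses a different denominator. Section 4.4.1.2 says that this chart displays frequency and percent, so its denominator can be recovered unless the count is zero.

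**5. Could there be post-baseline data?** First randomization was on 20 December 2022 and termination on 27 June 2023, 189 days (27.0 weeks) later. The latest randomization dates that allow a visit by termination are:
- nominal Week 24 (Day 168): 189 − 168 = 21 days after first randomization, so 10 January 2023
- SAP Week 24 window (from study day 128, that is 127 days on): 189 − 127 = 62 days, so 20 February 2023
- nominal Week 12 (Day 84): 189 − 84 = 105 days, so 4 April 2023

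These dates assume that follow-up stopped at termination and that dosing began on the day of randomization. The documents do not say when follow-up stopped, and they do not give the number randomized. Week 24 data were probably sparse. Even so, the planned by-visit plots and Week 24 listing provide for post-baseline values.

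**The case against.** The strongest reply is that the plan announces its own reduction. Section 4.1 says that the analyses were cut for lack of data, and its rule on change from baseline is prefaced as a general one. Appendix 2 does not promise tables, visits or change scores, and it names figures and listings among the supporting outputs. Observed-case plots are descriptive summaries, and with few patients, plots plus a listing are a defensible display. All of this stands, and it means that Appendix 2 is partly met rather than contradicted.

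A reader might go further and infer that the report contains no post-baseline efficacy, or that the data cannot be read, reused or pooled. The documents do not support that. Five figures and Listing 16.2.8 carry post-baseline values, and the bar chart shows counts and percentages. Week 24 change can be rebuilt from the listings for treated patients, and Protocol Section 11.6.3 makes individual patient data available on request.

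The reply does not explain why the simple summaries were dropped. Lack of data is a reason to omit multiple imputation, ANCOVA and the repeated-measures model. It is not a reason to omit n, mean and SD for values that are to be plotted and listed anyway.

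**Conclusion.** The point holds as a reporting gap. By title, all three efficacy tables are baseline only, and 0 of 36 outputs report change from baseline in HbA1c. The Appendix 2 statement and the Section 4.1 rule are met only in part, through figures of level or responder percentage and a Week 24 listing. No hypothesis test or conclusion depends on it, and the post-baseline data are not lost. It is still worth correcting, because the primary endpoint would otherwise have no numerical summary by arm.

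The conclusion rests on output titles. Table and figure shells are not in the documents, so a table might hold more than its title says, and a box plot might print n or quartiles.

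**What to change.** - Extend and retitle Tables 14.2.1.1 and 14.2.2 to show baseline, Week 12, Week 24 and change from baseline by arm on observed cases. Use the Section 4.1 statistics (n, mean, SD, median, Q1, Q3, minimum, maximum) and no hypothesis test. A confidence interval for the mean change is optional.
- Report HbA1c below 7.0% at Week 24 as n/N by arm with two denominators side by side: observed cases, and the Section 4.4.1.1 rule counting missing as not reached. Under that rule, patients stopped before Week 24 by the termination count as not reached, so the two may differ widely.
- If the tables are not extended, the minimum is to amend Appendix 2 to say that post-baseline efficacy is shown only in figures and a listing, and why.

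The cost is a modest amount of programming on two existing tables. Some cells may have a very small n, which the tabulated n makes visible.
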